Arterial blood pressure will be measured using an automated sphygmomanometer for the arm whilst the patient is seated after resting quietly for five minutes. Three measurements will be obtained for blood pressure and an average of the last two will be used. Standing blood pressure will also be collected. The measurement will be taken after the patient has been standing for three minutes with their feet hip-width apart and their arm supported at their side i.e. not hanging freely.

Demographics (Visit 0)

The date of birth, gender, race, smoking and drinking habits will be recorded by the doctor at the familiarisation visit (visit 0).

Medical History (Visit 0)

Details of any history of disease or surgical interventions will be recorded by the doctor at the familiarisation visit (visit 0).

Physical Examination (Visit 0)

A general physical examination will be performed by the doctor at the familiarisation visit (visit 0).

Randomisation to Study Medication (Visit 1)

At visit 1, participants will be randomised to either (i) Empagliflozin (Jardiance™) 25mg once daily, (ii) placebo once daily, (iii) Empagliflozin (Jardiance™) 25mg once daily and energy restriction diet, or (iv) placebo once daily and energy restriction diet using a web-based randomisation system supplied by the 3rd party company (Sealed Envelope Ltd.).

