*Other events that may not result in death, are not life threatening, or do not require hospitalisation, may be considered a serious adverse event when, based upon appropriate medical judgement, the event may jeopardise the patient and may require medical or surgical intervention to prevent one of the outcomes listed above.

Expected Serious Adverse Events/Reactions (SAE)

The most common adverse events associated with Empagliflozin (Jardiance™) are urinary tract and mycotic fungal infections (e.g. balanitis) and volume depletion leading to dehydration, postural hypotension and dizziness. If these events lead to hospitalisation of the participant, they will require immediate reporting to the study team. Otherwise, they will be treated as an AE and need reporting to the study team within 2 working days.

Abnormalities of renal and liver function will also be closely monitored as part of the usual study visits and any significant clinical deterioration in renal and/or liver function will be reported as an SAE. A serious deterioration in renal function to be classified as an SAE will be a reduction in eGFR to less than 30ml/min/1.73m². A serious deterioration in liver function will be classified as an SAE if ALT or AST is 3x greater than the upper limit of normal (ULN).

Ketoacidosis and Diabetic Ketoacidosis (DKA) have recently been reported as a possible serious SAE occurring with SGLT-2 inhibitor use by the US Food and Drugs Administration. Participants will be closely monitored for the development of this SAE and will be advised to seek medical attention immediately if they experience symptoms such as difficulty breathing, nausea, vomiting, abdominal pain, confusion, unusual fatigue or sleepiness, anorexia, excessive thirst, dehydration, low food intake, weight loss, infection, poor control of diabetes, and/or only moderately increased glucose levels.

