In patients where DKA is suspected or diagnosed, treatment with SGLT-2 inhibitors will be discontinued immediately. Restarting SGLT-2 inhibitor treatment in patients with previous DKA while on SGLT-2 inhibitor treatment is not recommended unless another clear precipitating factor is identified and resolved. Treatment will also be interrupted in patients who are hospitalised for major surgical procedures or acute medical illnesses. In both cases, treatment with SGLT-2 inhibitors may be restarted once the patient's condition has stabilised and only once the necessary safety assessments have been performed. The decision to stop or interrupt and subsequently re-start the study treatment Empagliflozin (Jardiance™) will be documented in the participant's medical notes. Any decisions regarding the withdrawal of participants from the study will be made by the study clinician and Principal Investigator. Further details about the discontinuation/withdrawal from, or interruption of, the study treatment can be found in Section 8.9, above (pg. 30).

Suspected Unexpected Serious Adverse Reactions (SUSAR)

A serious adverse reaction, the nature or severity of which is not consistent with the Summary of Product Characteristics for Empagliflozin (Jardiance™) will be reported as a SUSAR.

Adverse Events of Special Interests (AESI)

- Decreased renal function: creatinine value shows a ≥ 2 fold increase from baseline and is above ULN
- Hepatic injury defined by the following alterations of liver parameters after randomization at visit 1:-
 - Elevation of AST and/or ALT≥3 fold ULN combined with an elevation of total bilirubin≥2 fold ULN measured in the same blood draw sample
 - o Isolated elevation of AST and/or ALT≥5 fold ULN irrespective of any bilirubin elevation
- Diabetic Ketoacidosis (DKA)
 - O DKA is defined by the diagnostic criteria in the table below, and as defined by the American Diabetes Association (ADA).

Investigators should note that not all criteria in Table 2 (below) need to apply for the diagnosis of DKA, and clinical judgment should also be taken into consideration. Due to its mechanism of action, Empagliflozin (Jardiance™) may potentially modify the clinical presentation of DKA which may occur at lower plasma glucose levels than stated in the table below.

- Events involving Lower Limb Amputation

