10.2 Reporting Procedures for All Adverse Events

All AEs, including AESI, occurring during the study observed by the investigator or reported by the participant, whether or not attributed to study medication, will be recorded on the CRF and medical records.

The following information will be recorded: description, date of onset and end date, severity, assessment of relatedness to study medication, other suspect drug or device and action taken. Follow-up information should be provided as necessary.

AEs considered related to the study medication as judged by a medically qualified investigator or the Sponsor will be followed until resolution or the event is considered stable. All related AEs that result in a participant's withdrawal from the study or are present at the end of the study, should be followed up until a satisfactory resolution occurs. The duration of safety follow-ups will be at least five half-lives of the study medication. The half-life of Empagliflozin (Jardiance™) is 12.4 hours, thus the duration of safety follow-ups will be rounded up to be at least 72 hours (or 3 days).

It will be the investigator's clinical judgment whether or not an AE is of sufficient severity to require the participant's removal from treatment (see Section 8.9, pg. 30).

A participant may also voluntarily withdraw from treatment due to what he or she perceives as an intolerable AE. If either of these occurs, the participant must undergo an end of study assessment and be given appropriate care under medical supervision until symptoms cease or the condition becomes stable. The duration of safety follow-ups will be at least five half-lives of the study medication. The half-life of

Empagliflozin (Jardiance[™]) is 12.4 hours, thus the duration of safety follow-ups will be rounded up to be at least 72 hours (or 3 days).

The severity of events will be assessed on the following scale: 1 = mild, 2 = moderate, 3 = severe.

The relationship of AEs to the study medication will be assessed by a medically qualified investigator.

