5.5 Safety data

The number (%) of individuals experiencing either an adverse event or a serious adverse event will be summarised by randomised group.

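### SAP 5.5 plans only counts of people with an AE or SAE by arm; the protocol's events of special interest and named common drug events have no planned table

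*SAP*

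**What the plan says.** SAP 5.5 is a single sentence: "The number (%) of individuals experiencing either an adverse event or a serious adverse event will be summarised by randomised group". Protocol section 11 adds no adverse event analysis of its own.

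Protocol 10.1 sets up much more than this summary uses. It defines four adverse events of special interest (AESIs):

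- Renal: "Decreased renal function: creatinine value shows a ≥ 2 fold increase from baseline and is above ULN".
- Hepatic: "Hepatic injury defined by the following alterations of liver parameters after randomization at visit 1", followed by AST/ALT and bilirubin thresholds.
- DKA: "DKA is defined by the diagnostic criteria in the table below", with the note that not every criterion must apply and that clinical judgement counts.
- Lower limb amputation, defined by procedure.

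The same section names the drug's most common events: urinary tract and mycotic infection, and "volume depletion leading to dehydration, postural hypotension and dizziness". Protocol 10.2 has the CRF record "description, date of onset and end date, severity, assessment of relatedness to study medication" for every AE. Protocol 8.5 adds a postural measurement: "Standing blood pressure will also be collected".

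On who is analysed, Protocol 8.10 links most safety analyses to participants who received study medication. SAP 3.2 defines complete-case, multiple-imputation and per-protocol sets, but no safety set.

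SAP 5.2 does list eGFR, ALT and blood pressure as secondary outcomes. Under SAP 5.3.3 these are analysed by the primary-outcome approach, so each arm is compared with placebo.

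**The concern.** The protocol singles out specific risks, gives case definitions for some of them and has each event described and graded. The SAP then plans an output in which none of those categories appears. Someone who followed 5.5 to the letter would produce no count of any AESI by arm, no count of infections or volume-depletion events, and nothing on severity or relatedness.

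Two things are at stake. First, a proportion with any AE is driven by common, unrelated complaints, so a real excess of a non-serious drug event can look small or absent. Second, SAP 2.8 leaves the analysing statistician unblinded. If event tables are added later, the choice of which to show would be made with allocation known.

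DKA shows why the four-arm display matters. The amendment history ties exclusion criteria 18 to 21 to the DKA safety communication, and one of those criteria concerns conditions that limit eating. Two of the four arms prescribe energy restriction. Whether DKA occurred, and in which arm, is a question the protocol itself raises, and no planned table answers it.

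**Working it through.** **1. Size of the safety data set.** Inputs from Protocol 11.2: difference 120 pg/ml, SD 96.2 pg/ml, two-sided alpha 1.7%, power 80%, dropout 20%.

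- Normal approximation: n = 2 × (2.387 + 0.842)² × (96.2/120)² = 2 × 10.43 × 0.643 = 13.4, so 14 per arm.
- With the t distribution, 14 per arm gives 76.8% power and 15 gives 80.3%, so the plan's 15 is reproduced.
- Dropout: 15/(1 − 0.20) = 18.75, so 19 per arm, and 4 × 19 = 76.
- With 1:1:1:1 allocation, pooling over diet gives 2 × 19 = 38 on empagliflozin and 38 on placebo.

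**2. Where each risk appears.**

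| Risk | Protocol 10.1 | SAP 5.5 | Elsewhere in the SAP |
|---|---|---|---|
| Renal | AESI on creatinine; separate SAE rule at eGFR below 30 | in the total only | eGFR, secondary outcome |
| Hepatic | AESI on AST/ALT and bilirubin; SAE rule at ALT or AST above 3 × ULN | in the total only | ALT; AST and bilirubin not listed |
| DKA | AESI, Table 2 criteria plus judgement | in the total only | none |
| Amputation | AESI, by procedure | in the total only | none |
| Urinary and mycotic infection | among the most common events | in the total only | none |
| Volume depletion | among the most common events | in the total only | blood pressure, posture not stated |

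The eGFR, ALT and blood pressure analyses compare averages. They do not count people who cross a threshold, and one severe case is diluted in a mean over about 19 people. SAP 3.2.1 also makes them complete-case. Protocol 9.1 discontinues participants who cannot tolerate the drug, so some of those affected may lack later values.

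**3. The two readings of 5.5.** Protocol 10.1 makes every SAE an AE. Read as one figure, the words on SAEs add nothing and the output is a single any-event proportion per arm. Read as two rows (any AE, any SAE), the words do some work, and this is the more natural reading. Most of the serious risks would then fall in the SAE row: Protocol 10.1 treats DKA, eGFR below 30 and ALT or AST above 3 × ULN as SAEs, and refers to an SAE report for amputation. They would be counted there but not identified. The renal AESI and the renal SAE rule use different quantities, so one need not imply the other.

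**4. Dilution for non-serious events.** Let p0 be the share with some unrelated AE, q the placebo rate of the named event and d its excess on drug, all independent of the unrelated events. Then

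visible excess = [1 − (1 − p0)(1 − q − d)] − [1 − (1 − p0)(1 − q)] = (1 − p0) × d.

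The documents give no event rates, so p0 and d are assumptions:

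| p0 | d = 15 points | d = 10 points |
|---|---|---|
| 50% | 7.5 | 5.0 |
| 70% | 4.5 | 3.0 |
| 80% | 3.0 | 2.0 |

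In people: a 15-point excess in an arm of 19 is 0.15 × 19 = 2.9 participants. In the any-AE row it appears as 0.075 × 19 = 1.4 down to 0.03 × 19 = 0.6.

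**5. What event tables could show.**

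- Zero events, one-sided 95% upper bound 1 − 0.05^(1/n): 14.6% for n = 19 and 7.6% for n = 38.
- Chance of at least one event among 38 at an assumed true rate of 1%: 1 − 0.99^38 = 32%.
- Power for assumed infection rates of 5% versus 15%, two-sided 5%: about 17% (19 versus 19) and 30% (38 versus 38).
- With no placebo events, Fisher's exact test falls below 0.05 only from 5/19 in one arm or 6/38 pooled.

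These tables are therefore descriptive only.

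**The case against.** The strongest reply has four parts.

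- A reader might infer from 5.5 that it is the trial's only safety analysis and that none of the named risks can be compared. The documents do not support that. eGFR, ALT and blood pressure are compared with placebo, and event descriptions are on the CRF, so tables by event are possible. They are simply not planned. This part stands, and it limits the point to what is pre-specified.
- A reader might also infer that a DKA case would vanish among colds and minor complaints. That follows only if AEs and SAEs are pooled into one figure. On the two-row reading a DKA case sits in the SAE row, where minor events cannot hide it. This part stands too. The dilution in step 4 applies mainly to non-serious infection and volume-depletion events.
- The DSMC reviews unblinded AEs and SAEs, with safety reviews every six months. That is oversight during the trial and does not settle what the final analysis reports.
- This is a small Phase IV mechanistic trial of a drug used within its licence, with no safety objective, and any reader can add up arm counts to get drug versus placebo. The small numbers rule out formal testing, but they do not argue for merging the events. A reader can sum only categories that are shown, and 5.5 shows none.

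Two smaller cautions also stand. The protocol gives no purpose for the standing blood pressure, so its link to postural hypotension is an inference. And it speaks of participants receiving study medication, without setting a minimum number of doses.

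**Conclusion.** The point holds as a gap in pre-specification that should be closed. SAP 5.5 commits to AE/SAE counts by arm in ambiguous wording. It plans no table by arm for the four AESIs or the named common events, uses neither severity nor relatedness, and names no safety set. Renal and hepatic safety is otherwise covered only through mean eGFR and ALT, and volume status only through mean blood pressure.

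The size is moderate and rests on assumptions. For non-serious drug events, a 15-point excess would appear as 7.5 to 3 points if 50% to 80% of participants have an unrelated AE and the events are independent. It does not follow that the risks cannot be compared, or that a DKA case would go unseen. Neither the sample size nor the efficacy analysis is affected.

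**What to change.** Replace SAP 5.5 with descriptive counts of participants and of events, without tests:

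- any AE and any SAE, as separate rows;
- each AESI category as defined in Protocol 10.1;
- urinary infection, genital mycotic infection, and volume depletion or postural hypotension;
- severity, relatedness, and AEs leading to stopping study drug.

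Show each by the four arms and pooled as empagliflozin (two arms) versus placebo (two arms). Add to SAP 3.2 a safety set of participants who received study medication, in line with Protocol 8.10. Optionally, summarise the seated-to-standing blood pressure change and state in 5.2 which posture the blood pressure outcome uses.

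The cost is one SAP paragraph, one population definition and a few tables from data already collected; the sample size and conduct of the trial do not change. The downside is more rows, which must be labelled untested. The text should also say that absence of an event does not exclude a rare risk, given upper bounds of 14.6% per arm and 7.6% pooled when no event is seen.
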